**E. Aim 2 Focus groups Data Analysis**

We will use directed content analysis to summarize feedback on perceived polytobacco use risks and recommendations for refining CT messages.

Sample Size Justification: We will recruit up to 4 focus groups of size 6-8 LGBT polytobacco users (N = 24-32), a standard sample size in formative qualitative research.

**F. Aim 2 Eye-tracking (NCT0597294) Data Analysis**

*Hypothesis: Psychophysiological data will indicate that culturally targeted messages attract greater attention.*

Anti-polytobacco messages will be divided into text and graphic AOIs. Dwell time on the textual message (in milliseconds) is the primary eye-tracking outcome. We will use linear regression models to compare message type (CT vs NT) and framing (RR vs AR) on average dwell time and proportion of time viewing AOIs.

*Hypothesis: Exposure to targeted messages will result in greater perceived effectiveness of anti-polytobacco messages.*

Generalized linear models (GLMs) will be fit to examine differences in perceived effectiveness by message type (CT vs NT). Covariates will include baseline measures in applicable models and prior exposure tobacco communications. We will also investigate gender differences. Exploratory analyses: We will conduct exploratory analyses on secondary outcomes of interest. Specifically, we will fit generalized linear models (GLMs) to examine differences in EPPM constructs, risk perceptions, behavioral intentions, and 1-week recall by message type (CT vs NT).

Sample size justification: Virtual lab study. Differences in dwell time from eye-tracking antitobacco communications studies (PI: [name]) provide the basis for estimates. Assuming a 1.1 second standard deviation, 108 participants (n = 54 per arm) will provide a 95% chance of detecting an 0.6 second mean difference in dwell time on AOIs, at 80% power. Data from our prior tobacco warning studies indicate up to a 0.8 second difference in dwell time between conditions ([name], unpublished). A 0.6 second difference in dwell time is scientifically important as the brain can register stimuli within 0.03 seconds per fMRI. The enrollment number of n=300 will account for any duplicate responses, high abandonment rate for the I-motions portion of the survey after consent has been completed, and any low-quality eye tracking data recorded due to remote I-motions software.

*Research question: How does culturally targeting influence message recall?*

For quantitative survey responses, generalized linear models (GLMs) will be fit to examine differences in message recall by message type (CT vs NT). Covariates will include baseline measures in applicable models and prior exposure tobacco communications. We will also investigate gender differences.

For qualitative survey responses, we will summarize the feedback in response to each focus group question using rigorous and accelerated data reduction (RADaR) analytic methods. Used in applied research, RADaR organizes transcribed textual data from qualitative interviews into data tables; which are then organized and iteratively reduced, coded, and analyzed using team-based coding.

Sample size justification: All participants who complete the eye-tracking survey will be contacted to complete a one-week follow-up survey. Even with an estimated 30% attrition, the estimated analytic sample size (N=76) would be adequate for formative qualitative research.

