## C.2 Measurement / Instrumentation

For Aim 2 focus groups, a focus group guide will be developed and will be used to facilitate the research for preliminary work. Focus groups: Via semi-structured interview, we will ask participants about polytobacco use patterns, risk perceptions, and responses to CT messages.

For the Aim 2 eye-tracking experiment (NCT05972941), outcomes of interest are as follows:

Primary;	Attention	During exposure	Visual attention measured by eye-tracking on areas of interest (text, graphic): first fixation, dwell time (milliseconds), heat map
Primary;	Perceived effectiveness	Post-exposure to each message	Includes general perceived effectiveness (e.g., "The messages I received messages were worth remembering") and health-specific perceived effectiveness ("The messages I received made me concerned about the health effects of polytobacco use")
	EPPM Construct		Psychological reactance
Primary;	Risk Perceptions	Pre- and post-test	We will ask participants to report the significance, severity, and seriousness of health threats from tobacco use, absolute/relative risks of polytobacco use (and vs exclusive ENDS use)
Primary;	Behavioral Intentions	Pre- and post-test	Behavioral intentions to use tobacco; intentions quit all tobacco, intentions to switch to exclusive ENDS use
Secondary;	EPPM Constructs	Pre- and post-test	Self-efficacy to quit tobacco, response efficacy

For the 1-week follow-up a survey will be developed. Questions will quantitatively assess recent tobacco and ENDS use and health risk perceptions. Message recall will be assessed using quantitative and qualitative survey items.

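### Aim 2 eye-tracking trial: risk perceptions and behavioral intentions are primary in the outcome table but exploratory in the analysis section, and the power sentence gives both 95% and 80% for one comparison

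*Combined protocol and SAP*

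**What the plan says.** The outcome table in Section III.C.2 has separate rows reading "Primary; Risk Perceptions Pre- and post-test" and "Primary; Behavioral Intentions Pre- and post-test". Attention and perceived effectiveness carry the same label; self-efficacy and response efficacy are labelled secondary. The attention row lists several measures ("first fixation, dwell time (milliseconds), heat map"). The perceived-effectiveness row starts "Includes general perceived effectiveness" and adds a health-specific measure. The reactance row has no label of its own in the public text.

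Section VI.F states hypotheses only for attention and perceived effectiveness. It then says "We will conduct exploratory analyses on secondary outcomes of interest" and specifies models "to examine differences in EPPM constructs, risk perceptions, behavioral intentions, and 1-week recall by message type (CT vs NT"). For attention it says "Dwell time on the textual message (in milliseconds) is the primary eye-tracking outcome".

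The sample size paragraph of Section VI.F assumes an SD of 1.1 s and says that 108 participants, 54 per arm, "will provide a 95% chance of detecting an 0.6 second mean difference in dwell time on AOIs, at 80% power".

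**The concern.** The table and the analysis section give the same two outcomes different standing, and both are current text. If risk perceptions or intentions differ between arms, the table supports reporting a primary result and Section VI.F an exploratory one. The choice could then be made after the results are known. Section III.C adds a practical consequence: the more effective message set, targeted or non-targeted, goes forward to Aim 3, and no section says which Aim 2 outcome decides that.

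The power sentence is a smaller matter. A chance of detecting a given difference is power, so one comparison cannot have both 95% and 80%. A reader who takes the 95% at face value would overrate what a null dwell-time result rules out.

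**Working it through.** **1. Outcome roles, side by side**

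| Place | Attention | Perceived effectiveness | Risk perceptions | Behavioral intentions |
|---|---|---|---|---|
| III.C.2, outcome table | primary | primary | primary | primary |
| VI.F, analysis | hypothesis; text dwell time is the primary eye-tracking outcome | hypothesis | exploratory, secondary | exploratory, secondary |
| I, Aim 2 statement and hypothesis | named | named | not named | not named |
| III.C, statement of what Aim 2 is to determine | named | named | not named | not named |
| End of III.B.2, purpose of the R00 phase | named | not named | named | named |

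Section I and the aim statement in III.C fit VI.F. The R00 purpose paragraph fits the table on risk perceptions and intentions, and it omits perceived effectiveness. None of these three ranks the outcomes. Section III.C also lists all four among the things to be assessed, again unranked. Table 1 in Section III.A does not help: the text introduces it as presenting Aim 1 outcomes, so its silence on Aim 2 is expected.

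**2. Error rule**

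Aim 2 states no alpha, ordering or adjustment across outcomes. Holm's procedure appears in Sections VI.B and VI.D, both Aim 1, and covers pairwise comparisons within a model.

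**3. Power for dwell time**

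Inputs from VI.F: difference 0.6 s, SD 1.1 s, 54 per arm. Assumed: alpha 0.05, two-sided, as in the Aim 1 rating survey (VI.B).

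- Standardized difference: d = 0.6 / 1.1 = 0.545.
- Reproducing the plan's size: n per arm = 2(z₀.₉₇₅ + z₀.₈₀)² / d² = 2(1.960 + 0.842)² / 0.2975 = 52.8, so 53 by the normal approximation. The t-test solution is 53.74, so 54 per arm and 108 in total. **The plan's N reproduces exactly at 80%.**
- Power at 54 per arm: noncentrality = 0.545 × √(54/2) = 2.83, df = 106. Noncentral t gives 80.2% (normal approximation 80.9%).
- One-sided alpha 0.05: 87.9%. Neither version reaches 95%.
- Size needed for 95%: 2(1.960 + 1.645)² / 0.2975 = 87.4, so 88 by the normal approximation. The t-test solution is 88.33, so 89 per arm (178 in total). One-sided, the t-test solution is 73.44, so 74 per arm (148).
- Difference detectable with 95% power at 54 per arm, two-sided: about 0.77 s.

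**4. Scale of a multiplicity problem, as illustration only**

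With one unadjusted test per domain and independent tests, the chance of at least one false positive is 1 − 0.95² = 9.75% for two outcomes and 1 − 0.95⁴ = 18.5% for four. Positive correlation lowers both. If Bonferroni were used at 108 analysed, dwell-time power would be 71.2% (two) or 61.6% (four).

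**The case against.** Section VI.F can be read as the governing text. It carries the hypotheses, powers one outcome, and agrees with the Aim 2 statement in Section I. On that reading the table is simply over-labelled. This has weight, but the R00 purpose paragraph points the other way, and the table separates primary from secondary rows deliberately. Lost table formatting does not explain the conflict either, because the primary label sits on both disputed rows.

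It is also fair to say that the missing error rule is an omission, not a contradiction. Whether a rule is needed depends on how the roles are settled. With one primary outcome none is needed, and practice differs on adjusting across two separately stated hypotheses. That stands.

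Three stronger readings are tempting, and the documents support none of them:

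- *The Aim 2 error rate is inflated to a known level.* The illustrative percentages rest on an assumed alpha, an assumed number of tests and assumed independence. The Bonferroni powers also assume an adjustment that the plan does not propose. None is a bound, and none adds to the seriousness of the point.
- *The trial is too small.* 54 per arm is right for 80% power on the stated inputs. The 95% looks like a confidence level put in the wrong place, though the text does not confirm this.
- *Outcomes were relabelled in response to data.* Nothing in the text suggests it.

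**Conclusion.** The conflict over risk perceptions and behavioral intentions is real, is not settled elsewhere in the document, and leaves open which Aim 2 results are confirmatory. It should be fixed and is cheap to fix. The plan does not show which version was intended.

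The 95% figure is wrong as a detection probability: the design has 80.2% power for 0.6 s. This is a wording error with no effect on N = 108. It rests on two-sided alpha 0.05, equal arms, exactly 108 analysed and the stated SD. Section III.C.1 allows up to 300 to be enrolled to secure 108, so the number analysed could differ.

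Two loose ends belong to the same edit. Section VI.F makes dwell time on the text the primary eye-tracking outcome, but the power sentence refers to areas of interest, which comprise text and graphic. And reactance has no label in the table, while VI.F places EPPM constructs among the exploratory analyses.

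**What to change.** (a) Before outcomes are compared by arm, state one primary outcome list, identical in Sections III.C.2 and VI.F and consistent with Section I, the R00 purpose paragraph and Section III.C. Name the single measure that counts within each primary domain, and give reactance a role. Check the list against the registered outcomes for NCT05972941, which were not available here. Date and explain any relabelling: Section IV.F refers to participants who had already consented, so it would come after enrolment began. Which outcomes are primary is the investigators' choice. Text dwell time plus one perceived-effectiveness score is one option; keeping all four domains and amending VI.F is another.

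(b) Only if more than one primary outcome remains, state how they share the error rate. An ordered test with text dwell time first keeps its 80% power. Its price is that later outcomes are not confirmatory if dwell time fails. Aim 2 gives no SD, effect size or power for perceived effectiveness, so whether 108 is adequate for it as a second confirmatory outcome is unknown. If Holm or Bonferroni is preferred, report the resulting dwell-time power, which at 108 analysed can fall below 80%.

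(c) Restate the power sentence as: 80% power at two-sided alpha 0.05 to detect a 0.6 s difference in dwell time on the textual message (SD 1.1 s). The investigators should confirm alpha, sidedness, and that the SD applies to text dwell time and not to dwell time on all areas of interest.

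Cost: text edits only. Parts (a) and (c) leave the sample size unchanged, as does (b) with an ordered test so far as dwell time is concerned.

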## **VII. DATA SAFETY and MONITORING PLAN**

The Ohio State University Comprehensive Cancer Center Data Safety Monitoring Committee (DSMC) will be the DSMC of record and, thus, will be responsible for reviewing the study. The PI will submit a summary report of the study's progress, including all subsite activities and data status to the DSMC on an annual basis. All adverse events related to the study will be recorded by the investigators. The study investigators will evaluate adverse events and study data during their weekly meetings and make a determination of whether any adverse events affect the risk/benefit ratio of the study and whether modifications to the protocol (e.g., Potential risks) or consent procedures are required.

Serious unanticipated events are not anticipated. In the unlikely case that such serious adverse events occur, they will be reviewed by the OSUCCC – James Data and Safety Monitoring Committee (DSMC). All reportable serious adverse events will be reported within 48 hours to the OSU IRB and any appropriate funding and regulatory agencies. The investigators will specify whether the serious unanticipated adverse event is related to the study. Adverse events will be reported to the NCI when frequency and magnitude clearly exceed expectations.

The OSU IRB provides annual review of all open protocols and hence this is one level of monitoring that will occur. In this annual report, the investigator is required to report the number of subjects enrolled and treated, any adverse events that have occurred, and a summary of the findings from either the study or the literature that would affect the safety of the participants or the ethics of the trial. The PI will provide a summary of the Data Safety and Monitoring Plan annually as part of the progress report to the National Cancer Institute (NCI).

All data and safety monitoring will adhere to the policies and procedures of the OSU Comprehensive Cancer Center's Data and Safety Monitoring Plan which has been approved by NCI.

## **VIII. Dissemination Plan**

The study will be uploaded to clinicaltrials.gov and the results and accomplishments from this study will be made available to the public. We will disseminate the results and accomplishments from this trial to the research community and to the public at large through peer-reviewed scientific journal manuscripts and national conferences for the tobacco control, public health and medical communities. Additionally, the findings from this trial may be used to provide evidence informing the development of anti-tobacco messages for

---

THE OHIO STATE UNIVERSITY  
INITIAL APPROVAL: 03/05/2021  
LAST VERSION APPROVAL: 08/15/2023 (V7)  
VERSION APPROVAL: 11/20/2023

RESEARCH PROTOCOL V8  
PROTOCOL #: 2021C0020

national tobacco public education campaigns. Finally, members of our Community Advisory Board may receive study results and accomplishments.

